Subjective Refractive Error Determination: Subjects who meet all inclusion criteria for the study will be enrolled and be fitted in two different kinds of contact lenses throughout the course of the study. Before fitting the contact lenses, a subjective refraction will be performed to determine the best correction and contact lens power for the subject. The refraction will be performed by a licensed, trained optometrist ([name]) using a phoropter. Patient responses will be used to determine the final refractive error. This method is identical to refractive error determination in a regular eye exam.

Contact Lens Fitting: In this crossover trial, single vision Bausch + Lomb ULTRA® contact lenses and Bausch + Lomb ULTRA® for Presbyopia contact lenses will be fitted by a licensed optometrist. Bausch + Lomb ULTRA® and Bausch + Lomb ULTRA® for Presbyopia are FDA-approved daily wear soft contact lenses. All subjects will be habitual soft contact lens wearers, so no increased risk will be assumed by fitting the Bausch + Lomb ULTRA® contact lenses.

Anterior Ocular Segment Assessment: While the risk of contact lens complications (ocular inflammation, infection, etc.) in this study is extremely low, the anterior segment ocular health of both eyes of every subject will be assessed by a licensed optometrist at each visit to ensure no complications have occurred. This assessment will also include the ocular adnexa (lid margin and Meibomian glands). In the unlikely event that a complication does occur, the subject will be treated by a licensed optometrist and dismissed from the study.

c. Detailed Study Procedures

Overview

This randomized, prospective, crossover clinical trial will recruit uncomfortable, single vision, soft contact lens wearers in the non-presbyopic age range. The tenants of the Declaration of Helsinki will be followed. Complete inclusion criteria are listed in Table 1. Each subject will receive a single vision (Bausch + Lomb ULTRA®) and multifocal contact lens (Bausch + Lomb ULTRA® for Presbyopia) to wear for 2 weeks each. Subjects will be masked and randomly assigned to the first lens and then they will be crossed over to the remaining lens for the second 2-week period. Figure 1 displays a flow chart of the planned study procedures.

Subject Enrollment and Baseline Examination and Fitting

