Pre-presbyopes with symptoms of contact lens discomfort and asthenopia will be recruited from The Ohio State University College of Optometry Clinics. Interested subjects will be instructed to contact investigators by email. The Contact Lens Dry Eye Questionnaire-8 (CLDEQ-8), a survey validated to reflect change in opinion of contact lenses,¹¹ will be administered over the phone to ensure each subject has significant discomfort symptoms. Each subject must have a score of ≥ 12 points¹⁵ to qualify for the first, baseline examination.

At the baseline examination, inclusion criteria will be confirmed. The presence of concurrent dry eye or a binocular vision disorder (a group of disorders that involved how the eyes move together) will confound study results, so subjects with significant signs of these conditions will be excluded from the study (as defined in Table 1). With the each subject's habitual contact lens correction, heterophoria at distance and near and NPC will be measured to determine binocular vision eligibility. Accommodative function will also be assessed at this time. TBUT, ocular surface staining, and Schirmer testing will be performed to determine dry eye eligibility. Keratograph 5M tear imaging will also be performed at this time. A general anterior segment assessment will be made and assessment of the lid margins and Meibomian glands after habitual lens wear will be recorded. The CISS will be administered at the baseline examination. Subjects who meet all inclusion criteria will be enrolled and randomized (blocked randomization design with a 1:1 allocation ratio) to receive either the single vision Bausch + Lomb ULTRA® or single vision Bausch + Lomb ULTRA® for Presbyopia contact lenses first. All subjects who complete the baseline examination (whether enrolled or not) will receive \$40 cash and a parking pass.

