Each lens is made in only one size (base curve and diameter), so the main parameter determined during the fitting process will be power of the lens. For the single vision lens and multifocal lens, the power will be determine based on the spherical equivalent of the subject's refractive error. For the multifocal contact lens, subjects will receive a Low Add power in both eyes. Vision, fit, and comfort of the contact lens will be assessed in office on both eyes. Lenses will be allowed to settle on the eye for approximately 10 minutes before vision or fit are assessed. Once a satisfactory fit and visual endpoint has been achieved (patient is comfortable in lenses, binocular vision is better than 20/40, and examiner determines proper contact lens fit), the subject will be instructed to wear the lenses daily for the next 2 weeks. Accommodative testing and heterophoria measurements with the first dispensed lens pair will be performed. Subjects will be instructed not to sleep in the contact lenses and to remove them each night to clean and soak and Biotrue® contact lens solution. A clean contact lens case and Biotrue® solution will be provided to each subject. Subjects will be given the contact information of the PI and instructed to contact investigators if they experience any signs of complications (redness, discharge, irritation, pain, etc.). Before leaving the baseline examination, each subject will schedule an appointment for the second examination approximately 2 weeks from the initial baseline examination date (no sooner than 2 weeks, no later than 3 weeks). The Bausch + Lomb ULTRA® contact lenses are FDA-approved for daily wear. Subjects will receive \$40 cash and a parking pass at the end of the baseline examination.

[figure not shown]

Figure 1: Flow chart of study procedures for randomized crossover clinical trial (Please see Data Analysis and Sample Size Justification section for updated sample size numbers)

Second Examination and Fitting

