Subjects will be asked which of the two trial lens pairs they preferred and be asked which lens (single vision or multifocal) they think they had first and second. After all testing and procedures have been completed, subjects will be instructed to return to habitual contact lens wear and informed of what lenses they had during the first and second trial periods. Subjects will receive \$40 cash and a parking pass at the end of the third examination.

Data Analysis and Sample Size Justification

Paired *t* tests will be performed to compare mean CLDEQ-8 scores with habitual single vision lenses, single vision Bausch + Lomb ULTRA® contact lenses, or Bausch + Lomb ULTRA® for Presbyopia contact lenses to one another. Repeated measures ANOVA testing will be performed to determine if contact lens comfort (CLDEQ-8 score) is affected by age or magnitude of myopia when subjects are corrected with their habitual single vision lenses, single vision Bausch + Lomb ULTRA® contact lenses, or ULTRA® for Presbyopia contact lenses. CISS scores throughout the trial will be analyzed in the same way as the CLDEQ-8 scores. To determine if accommodative ability is related to multifocal preference, paired *t* tests will be used to compare contact lens preference (single vision versus multifocal) to initial accommodative function (lag/lead) values.

In order to detect a conservative standardized effect size of 0.6 ($\alpha = 0.05$, $\beta = 0.20$), a sample size of 45 subjects would be necessary. A previous cross-over trial utilizing the CLDEQ-8 reported a 20% loss-to-follow-up rate.¹¹ Anticipating and accounting for a similar rate in our subject enrollment, a sample of 54 subjects would be appropriate. Because the hypotheses of this study have never been tested, we recognize that this initial sample size may seem inadequate after all data is collected. So, our initial 54-subject sample size will be increased by an additional 25% to allow for additional data collection that may be necessary. Therefore, 68 subjects (34 subjects per group) will be sought for IRB approval to account for the possibility of needing more subject data to make reliable study conclusions.

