Updated sample size (03/07/2017): At this point in the study, we have seen 26 total subjects: 17 were successfully enrolled and 9 failed to qualify for the study (did not meet all dry eye and binocular vision inclusion criteria) after completing the baseline examination. Therefore, approximately 35% of the subjects who have participated in baseline examinations have failed. With 17 subjects enrolled, we need to recruit and enroll an additional 51 subjects to complete the study. Considering our recent experience with enrollment, we will assume that 35% of these 51 baseline examinations (or about 18) will not qualify for the study. Therefore, we are requesting to increase our original sample size of 68 subjects by 18 and recruit a sample size of 86 (43 subjects per group).

Updated sample size (8/14/2017): Upon initial data analysis of the subjects who have completed the study, we found an interaction between subject age group and change in CLDEQ-8 survey score that, while not statistically significant ($p = 0.12$), was clinically significant (an approximate 4-point difference between age groups) according to CLDEQ-8 interpretation. We have hypothesized that this clinically relevant finding may have lacked statistical significance because of an inadequate sample size. Because of the lack of software or well-developed methods for calculating the sample size for an interaction in a cross-over study, a simulation study was conducted to estimate what a sufficient sample size would be. The simulation assessed adding more subjects to the sample – using

the subjects currently in the sample. This iterative process was conducted to draw 10 different samples from which sample size was estimated in order to attempt to replicate the original finding with greater power. Given the simulation, it was recommended that 30 additional subjects be tested. At this point, approximately 27% of subjects who present for the baseline examination fail to qualify for the study, so we will increase the 30 additional subjects by 27% (8 subjects) and, therefore, increase our overall sample size by 38 subjects. In conclusion, the new number of recruited participants will increased from 86 to 124.

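### The age and myopia analysis spans three lenses, one of them not randomised, and names no test on the randomised multifocal-versus-single-vision difference, so a general new-lens response could be read as a differential multifocal effect

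*Combined protocol and SAP*

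**What the plan says.** Under Data Analysis and Sample Size Justification, the repeated measures ANOVA asks whether CLDEQ-8 comfort "is affected by age or magnitude of myopia when subjects are corrected with their habitual single vision lenses" or with either study lens. CISS is to be analysed the same way. The section names no lens-by-age or lens-by-myopia interaction, no contrast between particular lenses within the ANOVA, and no rule for interpreting a positive result. It does plan paired t tests between each pair of lenses, but not by age or myopia.

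The Overview of the Detailed Study Procedures limits randomisation to the two study lenses: "Subjects will be masked and randomly assigned to the first lens and then they will be crossed over to the remaining lens". The baseline section adds that this is a "blocked randomization design with a 1:1 allocation ratio".

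The only habitual-lens CLDEQ-8 described is the screening score, which "will be administered over the phone to ensure each subject has significant discomfort symptoms" and must be at least 12. The baseline visit lists the CISS but no repeat CLDEQ-8. The study-lens scores are collected at the second and third clinic visits. For the study lenses, "A clean contact lens case and Biotrue® solution will be provided to each subject", and this is repeated at the second fitting.

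The sample size update of 8/14/2017 reports an "interaction between subject age group and change in CLDEQ-8 survey score" of about 4 points (p = 0.12). It adds 30 subjects to be tested because of it, and does not say which two lenses the change compares.

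**The concern.** The objective is how multifocal lenses affect comfort, so the useful subgroup question is whether multifocal optics help some ages or degrees of myopia more than others. Only the comparison of the two study lenses isolates optics under randomisation and masking. A change from the habitual lens also carries a new lens, a new case, supplied care solution, a different mode of questioning and the wearer's expectation.

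An interaction test over three lens levels has 2 degrees of freedom. It responds to any difference between subgroups in lens profile, including one where single vision and multifocal move together and only the habitual score stands apart. Without a named contrast, a significant result could be attributed to the multifocal lens when it reflects a general response to study lenses. The age part matters most, because an interaction with age group led to the August 2017 increase in sample size.

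**Working it through.** **The plan's own figures.** The stated 45 subjects (effect size 0.6, α 0.05, power 0.80) reproduces as a per-group size for two independent groups: 2 × (1.96 + 0.84)² / 0.6² ≈ 44, or 44.6 with the t distribution. It is not a calculation for an interaction, and nothing below depends on it. The August 2017 simulation cannot be reproduced from what is given.

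**Inputs**
- Total N: 54 and 84. The 11/21/2017 update gives 69 enrolled, 15 of them in the new round, so 69 − 15 = 54 before it; 54 + 30 = 84 after the planned addition.
- D, the extra improvement of one age group on both study lenses: 4 points (the size of the interim gap) and 2 points. Both are assumptions; the documents report no such general difference.
- SD of a paired CLDEQ-8 difference: not given; 5, 7 and 9.3 assumed.
- Two equal age groups, equal correlation between lenses, normal errors, two-sided 5%, no selection on the habitual score.

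**What SD does the interim result suggest?** If the 4-point gap with p = 0.12 compared change scores in two equal groups, SE = 4 / t and SD = SE / √(4/n).

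| Subjects analysed | t | SE | Implied SD |
|---|---|---|---|
| 30 | 1.604 | 2.49 | 6.8 |
| 40 | 1.591 | 2.51 | 8.0 |
| 54 | 1.581 | 2.53 | 9.3 |

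The number analysed is not stated. An SD of 5 would need only about 17 subjects to give p = 0.12.

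**Three-lens interaction test when multifocal and single vision do not differ by age group.** The group differences over habitual, single vision and multifocal are (0, D, D). Their squared deviations from the mean sum to (2/3)D². With error variance SD²/2 per score, the noncentrality is

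λ = (N/4) × (2/3)D² / (SD²/2) = N·D² / (3·SD²),

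and F has 2 and 2(N − 2) degrees of freedom. Example: N = 54, D = 4, SD = 9.3 gives λ = 54 × 16 / (3 × 86.49) = 3.33 and a rejection rate of 34%.

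| N | SD | D = 4 | D = 2 |
|---|---|---|---|
| 54 | 5 | 86% | 30% |
| 54 | 7 | 56% | 17% |
| 54 | 9.3 | 34% | 12% |
| 84 | 5 | 97% | 45% |
| 84 | 7 | 77% | 25% |
| 84 | 9.3 | 51% | 16% |

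Simulation with 10,000 trials per cell agrees to within about 1 point. In the same simulated data, the group comparison of the multifocal-minus-single-vision difference rejected in about 5% of trials in every cell. A multifocal-minus-habitual change score behaved like the three-lens test (34% to 95% for D = 4).

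**Power given up.** If a true 4-point effect sits in the multifocal lens alone, the three-lens test has the same λ as above. The two-lens contrast has λ = N·D² / (4·SD²) on 1 and N − 2 degrees of freedom.

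| N | SD | Three lenses | Two-lens contrast |
|---|---|---|---|
| 54 | 5 | 85.9% | 82.2% |
| 54 | 7 | 56.2% | 54.0% |
| 54 | 9.3 | 34.4% | 34.2% |
| 84 | 5 | 97.2% | 95.2% |
| 84 | 7 | 77.0% | 73.5% |
| 84 | 9.3 | 51.1% | 49.5% |

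The loss is between 0 and 4 percentage points.

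**The case against.** The strongest reply is that the design already holds the control that is needed. The single vision study lens comes with the same new case and solution. If one age group simply responds more to study lenses, its single vision and multifocal means move together and the three-lens results will show it. This stands: a reader might infer that the trial cannot separate the two explanations, and that would be wrong. The data can separate them; what is missing is a stated test that does.

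A reader might also infer that a positive result will be taken as a multifocal effect. The data analysis section states no interpretation and does not name an interaction; it could mean a main effect of age or myopia. Only the possibility of misreading is supported. But a main effect alone would not address differential multifocal benefit, so the wording needs settling either way.

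A third tempting inference is that the August 2017 interaction was itself computed from the habitual lens. The update does not show this. It speaks of an interaction in a cross-over study, and only the two study lenses are crossed over, so the randomised difference fits at least as well. The text leaves it open. That update also concerns age group only; no subjects were added on account of myopia.

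Finally, the documents offer no evidence of a 4-point age difference in general response among 30- to 40-year-olds, so the rejection rates are conditional on one existing.

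**Conclusion.** The point holds as a gap in specification. The age and myopia analysis covers three lens conditions, one of them outside the randomisation and measured differently, and no contrast on the randomised pair is tied to age or myopia. Run as a three-lens interaction test, it would reject in about 34% to 97% of trials for a purely general 4-point difference, and 12% to 45% for 2 points, at 54 to 84 subjects.

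The SDs of 5 to 9.3 are assumptions. The values nearer the interim result, 7 to 9.3, give about 34% to 77% for 4 points and 12% to 25% for 2 points, and are more plausible. That inference itself assumes 30 to 54 subjects analysed in two equal age groups. The direction does not depend on the SD: a shift confined to the habitual score cannot enter the multifocal-minus-single-vision contrast, which keeps its nominal 5% level. Nor does it depend on selecting subjects with high habitual scores, since no selection was imposed.

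**What to change.** - For CLDEQ-8 and CISS, make the interpretive test for age, and separately for myopia, its interaction with the within-subject difference between the two randomised lenses (single vision ULTRA minus multifocal). Write this down before the final analysis.
- Keep the habitual-lens comparisons, labelled as non-randomised and descriptive.
- State which lenses the change score in the 8/14/2017 update compares. If it was a change from the habitual lens, re-run that age-group interaction on the randomised difference and report both.

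This needs changes of wording and possibly one re-analysis, with no new data or visits. The price is about 0 to 4 percentage points of power if a true effect is confined to the multifocal lens.

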NPC: NPC is a routine clinical measurement that assesses the ability of the eyes to converge and accommodate while viewing a near target.¹⁴ NPC will be evaluated binocularly with the subject's habitual correction using a push-up technique. An accommodative target (20/30 near letter) on a fixation stick will be slowly moved closer towards the subject's central visual axis until the subject experiences constant diplopia. The distance from the bridge of the subject's nose to this point will be recorded as the break point. Subjects with a break point of 6 cm or higher will be excluded from the study.

Accommodative Function: Accommodative function (lead/lag), or the ability of the subject to focus when reading, will be measured with an autorefractor. The autorefractor is a non-contact instrument that measures refractive error. Subjects will wear their habitual contact lens correction. Accommodative response will be measured at two stimulus levels with each pair of contact lenses (habitual, single vision, and multifocal) (2.00 and 4.00 diopters) to determine how accurately the subject focuses on letter visual targets at various distances while corrected with different contact lenses.

Dry Eye Testing: Subjects who have significant signs of dry eye will be excluded from the study. Basic dry eye testing, similar to that performed during a regular eye exam, will be performed to ensure subjects with dry eye do not confound study results. Tear break-up time (TBUT), ocular surface staining, and Schirmer test will be performed at the baseline examination. All dry eye tests will be performed on the right eye only.

TBUT: TBUT measurements are commonly used to assess severity of dry eye. The measurement quantifies the time it takes for the tear film to break-up on the ocular surface after a complete blink. To measure TBUT, fluorescein sodium will be instilled in the inferior palpebral conjunctiva using with a Barnes-Hind Ful-Glo Fluorescein Sodium Ophthalmic Strip that has been wetted with a drop of non-preserved saline. After instillation, the subject will be placed in a slit lamp and

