Updated Sample Size (11/21/2017): At this stage in the study, we have successfully enrolled 69 subjects, and 35 subjects have failed to qualify for the study after completing the baseline examination. In total, we have recruited 104 of the 124 approved subjects for this study. The 27% baseline examination failure rate we observed during the first recruitment stage has increased to 66%. Specifically, since beginning this new round of recruitment, we have enrolled 15 subjects in the study and had 15 baseline examination failures (making our total recruitment at 104 subjects). In order to enroll the 30 additional subjects described above (on 8/14/2017) and allow for anticipated baseline examination failures, we will increase the number of recruited participants from 124 to 144.

Timeline

We anticipate that the data collection portion of this project will take 6 to 7 months to complete. At the time of this protocol submission, we can anticipate that IRB approval and all other contractual agreements will be finalized and approved by mid-December 2016. At this time, we will aggressively start recruitment by advertising in the OSU College of Optometry, OSU Medical and OSU Main Campuses. We will also send postcards to OSU College of Optometry Contact Lens Clinic patients.

[figure not shown]

Table 2: Timeline of study activities

We expect that recruitment and enrollment of all 54 subjects will take 5 to 6 months (ending in May 2017). This estimate accounts for slower anticipated recruitment (5-10 subjects per month) in December due to the holidays. Recruitment rates starting in January 2017 are anticipated to be higher (10-15 subjects per month). [name] will be spending approximately 30 hours per week recruiting subjects and performing examinations and organizational study tasks during the data collection portion of the study. If we estimate that each subject will require approximately 5 hours of total examination time throughout the course of the entire study, she will have sufficient time budgeted to complete all recruitment and data collection. All data collection is projected to be complete before July 2017. Table 2 shows a projected timeline of study activities.

IV. References

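### The lens-preference analysis names paired t tests, but each subject gives one preference, so the two preference groups are different people and cannot be paired

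*Combined protocol and SAP*

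**What the plan says.** The aim and the method stand in one sentence of the Data Analysis and Sample Size Justification section. It opens with "To determine if accommodative ability is related to multifocal preference, paired" and continues: "paired *t* tests will be used to compare contact lens preference (single vision versus multifocal) to initial accommodative function (lag/lead) values".

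The two variables come from different visits:

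- **Preference.** Third and Final Examination: "Subjects will be asked which of the two trial lens pairs they preferred". This is a single question with one answer per subject.
- **Initial lag/lead.** Subject Enrollment and Baseline Examination and Fitting, in the account of testing in habitual lenses before randomization: "Accommodative function will also be assessed at this time". The Accommodative Function paragraph adds "Subjects will wear their habitual contact lens correction" and then "Accommodative response will be measured at two stimulus levels with each pair of contact lenses", the levels being 2.00 and 4.00 dioptres and the lenses being habitual, single vision and multifocal.

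No section matches subjects who prefer one lens with subjects who prefer the other. No unpaired test, regression or other method is given for this question.

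**The concern.** A paired t test analyses differences between two values of one measurement taken on the same unit or on matched units. Preference sorts subjects into two groups that do not overlap, so there is no second value to subtract. The same paragraph uses paired t tests for CLDEQ-8, where every subject has a score in each lens and the pairing is real. The term appears to have been carried over to a question with a different structure.

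The rationale of the trial is that weak accommodation contributes to contact lens discomfort. This sentence is the plan's only stated analysis that sets measured accommodation against the response to the multifocal lens. An analyst following it must either run a test that does not apply or choose another once the data are in. The sample size update of 8/14/2017 reports that outcome data had already been analysed during the study, so a method chosen now should be fixed in writing.

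**Working it through.** **1. Data per subject**

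| Variable | When | Values per subject |
|---|---|---|
| Lens preference | Third examination | 1 category |
| Lag/lead in habitual lenses | Baseline | 2 (at 2.00 D and 4.00 D) |
| Lag/lead in each trial lens | At dispensing and after about 2 weeks | 2 stimulus levels each time |

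**2. Pairings that might rescue the sentence**

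- *Single-vision preferrers with multifocal preferrers.* These are different people, generally in unequal numbers, and no matching is described. Number of pairs: 0.
- *A subject's lag in single vision with the same subject's lag in multifocal.* This is a valid pair, but it compares lenses and does not involve preference.
- *A subject's 2.00 D reading with the same subject's 4.00 D reading.* This is a valid pair, but it compares stimulus levels and does not involve preference.
- *A subject's preference with the same subject's lag.* A category cannot be subtracted from a dioptre value.

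A fifth pairing, preferred lens against non-preferred lens, is taken up under the objection.

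**3. Does the plan's sample size relate to this analysis?**

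The plan gives no figure for the preference question. Its only computed size is 45 subjects, for a standardized effect of 0.6 with α = 0.05 and β = 0.20. Taking the test as two-sided, a two-sample t test gives 44.6, so 45 *per group*. The plan uses 45 as a total and does not connect it with preference.

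**4. What the fitting test could detect (context only)**

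Enrolment comes from the update of 11/21/2017. It reports 69 enrolled, says "since beginning this new round of recruitment, we have enrolled 15 subjects in the study", and sets the new ceiling "In order to enroll the 30 additional subjects described above".

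- Still to enrol: 30 − 15 = 15. Planned total: 69 + 15 = 84.
- With the plan's 20% loss: 0.8 × 84 = 67.2, about 67. Subjects lost before the third examination give no preference.

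For groups of n₁ and n₂, the smallest detectable standardized difference at two-sided 0.05 and 80% power is approximately

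d ≈ (1.960 + 0.842) × √(1/n₁ + 1/n₂).

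For 42/42 this is 2.802 × √(2/42) = 0.611. The noncentral t calculation with equal variances gives slightly larger values. The splits are assumptions; the documents give none.

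| Subjects with a preference | Split | Detectable difference (SD) |
|---|---|---|
| 84 | 42/42 | 0.619 |
| 84 | 56/28 | 0.656 |
| 84 | 67/17 | 0.770 |
| 67 | 34/33 | 0.695 |
| 67 | 45/22 | 0.740 |
| 67 | 54/13 | 0.879 |

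The total of 84 is itself a reading of the update. The ceiling of 144 leaves 144 − 104 = 40 baseline examinations. If half qualify, as with 15 of the last 30, about 20 more enrol, giving 89. At the stated 66% failure rate, 40 × 0.34 ≈ 14 more enrol, giving 83. At an even split this moves the detectable difference only between about 0.60 and 0.62 SD.

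**The case against.** The best counter-argument is that one pairing does bring preference in. Each subject has lag/lead in both trial lenses, so one could take lag in the preferred lens minus lag in the non-preferred lens and test that difference with a paired t test. On that view, initial would mean the reading at dispensing rather than the one two weeks later. It is a legitimate within-subject test, so it would be too strong to say that no pairing of a subject's own readings could involve preference.

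As a reading of the sentence it does not hold. The stated aim concerns the subject's accommodative ability, and the stated contrast is single-vision preference against multifocal preference. The preferred-minus-non-preferred difference would also mix the multifocal lens's own optical effect on measured lag with the subject's ability.

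Other points are fair:

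- The baseline visit also includes accommodative testing in the first dispensed lens, so initial leaves the lens slightly open as well as the stimulus level. The habitual-lens reading is the natural one, because it is taken before randomization and is the same condition for everyone.
- Logistic regression of preference on baseline lag would serve as well as a Welch test.
- The detectable differences describe the replacement test, not harm done by the paired wording. They assume equal variances, which Welch does not require.
- This is one supporting analysis, no data are lost, and unequal group sizes would expose the problem at the analysis stage.

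These points limit the weight of the finding. They do not make the named test usable.

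**Conclusion.** The concern holds. As written, the test cannot answer the question it is assigned to, because the preference groups are independent and the plan names nothing else. The conclusion rests on the data structure and on no numerical assumption.

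Its reach is one supporting analysis. It should be fixed, because it is the only planned use of measured lag/lead. A smaller gap remains beside it: two stimulus levels are measured and neither is named as the main one, so correcting the test alone would leave a choice of outcome open.

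The unpaired comparison would detect only moderate to large differences, about 0.62 to 0.77 SD with 84 subjects and 0.70 to 0.88 SD with 67. Those ranges depend on the assumed splits, equal variances and the enrolment reading above. A null result should therefore not be taken as evidence of no relation.

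**What to change.** Replace the sentence with one that specifies:

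- an independent-samples (Welch) t test of baseline lag/lead, measured in habitual lenses, between subjects who prefer single vision and subjects who prefer multifocal;
- the result reported as a mean difference with a 95% confidence interval;
- either the 2.00 D or the 4.00 D reading as the main one, with the other supportive.

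The same sentence can usefully say how an answer of no preference is handled, since the plan does not mention one.

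The cost is one sentence in the analysis section. Preference and habitual-lens baseline lag/lead are already collected, so no visit, measurement or sample size changes.
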